#### 8.1. Planned recruitment

Cohort 1 has already provided their data (n ~173,000) in response to the UK Biobank pain rephenotyping exercise. PAINSTORM has approval to access the phenotypic and genetic data that are available for all participants.

Cohort 2 includes approximately 18,000 individuals with diabetes, and an estimated 600 who have received potentially neurotoxic chemotherapy. We aim for a response rate of 33.3% (consistent with the baseline response rate in GoDARTS during the DOLORisk study), which will generate study samples of 5,994 and 200 respectively.

Cohort 3 includes approximately 1,000 people with diabetes who participated in baseline and follow-up surveys for DOLORisk. We aim for a response rate of 67% (consistent with the follow-up response rate in GoDARTS during the DOLORisk study), which will generate a sample of 667 participants in whom NeuP progress can be tracked over 5 years at three time points.

## 8.2. Sample size calculation

Cohort 1: Assuming a NeuP prevalence of 10% in the general population and 25% in the diabetic population (painful diabetic peripheral neuropathy [DPN]), we will have a sample size of 17,300 NeuP cases and 155,700 no-NeuP controls in the UK Biobank, with 2,714 having painful DPN and 8,141 without painful DPN.

Cohort 2: Assuming the same NeuP prevalence in the diabetic population and a prevalence of 30% in the chemotherapy population (painful CIPN), we will have a sample size of 1,499 painful DPN and 1,600 without painful DPN in SHARE, and 60 with painful CIPN and 140 without painful CIPN.

Cohort 3: In the first DOLORisk questionnaire (which is being used as baseline), 482 participants had NeuP and 1,094 had no-NeuP in GoDARTS, and 45 participants had painful DPN and 130 without painful DPN.

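### Section 8.2 projects 1,600 SHARE respondents without painful DPN, but the protocol's own sample of 5,994 and prevalence of 25% leave 4,495

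*Protocol*

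**What the plan says.** Section 8.1 sets the size of Cohort 2: "Cohort 2 includes approximately 18,000 individuals with diabetes, and an estimated 600 who have received potentially neurotoxic chemotherapy". It then gives the target, "We aim for a response rate of 33.3"%, "which will generate study samples of 5,994 and 200 respectively". The Study Summary agrees, with a planned Cohort 2 sample of 6,194 = 5,994 + 200.

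Section 8.2 turns these samples into projected case and control counts. Under Cohort 1 it assumes a painful DPN prevalence of 25% among people with diabetes. Under Cohort 2 it carries that prevalence over and adds 30% for painful CIPN after chemotherapy. The diabetes result for Cohort 2 is "we will have a sample size of 1,499 painful DPN and 1,600 without painful DPN in SHARE". The chemotherapy result, in the same sentence, is "60 with painful CIPN and 140 without painful CIPN". For people with diabetes in UK Biobank the section projects a split "with 2,714 having painful DPN and 8,141 without painful DPN".

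**The concern.** The number without painful DPN should be what remains of the diabetes sample once the projected cases are removed. The printed 1,600 is far below that, although the case count beside it follows exactly from the stated sample and prevalence. Section 8.2 gives no significance level, power or effect size, so the case and control counts are all it offers on sample size. Section 8 plans case-control genetic studies that include SHARE. A reader judging what that cohort can contribute would take from section 8.2 a nearly balanced group of about 3,100, when the protocol's own inputs describe about 6,000 with three controls to each case.

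**Working it through.** **Inputs**
- SHARE members with diabetes: about 18,000 (section 8.1)
- Cohort 2 response rate: 33.3% (section 8.1)
- Prevalence of painful DPN: 25% (section 8.2, Cohort 1, carried over to Cohort 2)
- Printed split: 1,499 with and 1,600 without painful DPN (section 8.2)

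**Figures that reproduce**
- Sample = pool × response rate: 18,000 × 0.333 = 5,994, as printed.
- Cases = sample × prevalence: 5,994 × 0.25 = 1,498.5, printed as 1,499. This shows that 5,994 is the denominator behind the case count.

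**Figure that does not reproduce**
- Non-cases = sample × (1 − prevalence): 5,994 × 0.75 = 4,495.5. The whole number that adds with 1,499 to 5,994 is 4,495.
- Printed: 1,600, and 1,600/4,495 = 36% of that.

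**What the printed pair implies**
- Total: 1,499 + 1,600 = 3,099.
- Prevalence: 1,499/3,099 = 48.4%, against the assumed 25%.
- Respondents unplaced: 5,994 − 3,099 = 2,895.
- Working back from 1,600 as 75% of a sample: 1,600/0.75 = 2,133 respondents and 533 cases. That contradicts both 5,994 and 1,499.

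Other routes to 1,600 were tried: samples of 6,000, 6,194 and 18,000; prevalences of 10%, 30%, 33.3% and 67%; and a second application of the response rate to the non-cases. None gives 1,600.

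**Other splits in section 8.2**

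| Group | Sample | Prevalence | Expected split | Printed split |
|---|---|---|---|---|
| UK Biobank, all | 173,000 | 10% | 17,300 / 155,700 | 17,300 / 155,700 |
| UK Biobank, diabetes | 2,714 + 8,141 = 10,855 | 25% | 2,714 / 8,141 | 2,714 / 8,141 |
| SHARE, chemotherapy | 200 | 30% | 60 / 140 | 60 / 140 |
| SHARE, diabetes | 5,994 | 25% | 1,499 / 4,495 | 1,499 / 1,600 |

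The 10,855 in the second row is the sum of the printed pair, so that row shows only that the split is 25/75.

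Cohort 3 is of a different kind. Its 45 with and 130 without painful DPN total 175, while the same paragraph counts 482 + 1,094 = 1,576 participants with and without NeuP. These are observed baseline counts, not projections from a prevalence, and they do not cover the whole cohort.

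**Size of the discrepancy**
Effective case-control size = 4/(1/cases + 1/controls):
- As printed: 4/(1/1,499 + 1/1,600) ≈ 3,096
- With the complement: 4/(1/1,499 + 1/4,495) ≈ 4,496
- Ratio: 4,496/3,096 = 1.45

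**The case against.** The best defence of 1,600 is that it may describe a restricted control group. Section 8.5 separates painful neuropathy, painless neuropathy and no neuropathy, so the controls might be, for example, people with painless DPN only. The Cohort 3 counts show that, in this section, those without painful DPN are not always everyone else in the cohort. This leaves the origin of 1,600 open. A reader might infer that 1,600 is proved to be a slip and that 4,495 must be right; the documents do not go that far. They show that 1,600 cannot be reconciled with 5,994 and 25% as written, and they state no matching, control sampling, genotype or phenotype restriction for Cohort 2. The slip remains the more likely explanation, because every other projected split is a full complement, including the one in the same sentence.

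The second defence concerns consequence, and it stands. Section 8.4 declares all outcomes exploratory, with no unified primary or secondary endpoint. The recruitment targets of 5,994 and 6,194 do not depend on 1,600, and nor do eligibility or the invitation process. A reader might infer that the study is underpowered or that the genetic analyses would be distorted. Neither follows: no power claim rests on the figure, the analyses will use the cases and controls actually observed, and if the complement is meant the cohort has more controls than stated.

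**Conclusion.** The contradiction holds. On the protocol's own inputs the Cohort 2 diabetes split is 1,499 and 4,495, and the printed 1,600 leaves 2,895 of 5,994 expected respondents unplaced. What is misstated is a projected control count, and with it the apparent information in the SHARE case-control comparison: an effective size of about 3,096 as printed against about 4,496, some 45% more.

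The arithmetic uses only figures printed in the protocol. The figure of 4,496 also assumes that all respondents without painful DPN serve as controls and that everyone can be analysed. Section 7.4 says that linked data, including genetics, are collected only where available, so the genetic comparison may be smaller. With no significance level, power or effect size in the protocol, no detectable effect can be derived from either count. This is a should-fix correction.

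**What to change.** Reconcile 1,600 with 5,994 and 25% in section 8.2:

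- If all respondents without painful DPN are meant, change 1,600 to 4,495.
- If 1,600 is a restricted control group, state the restriction and how the number was reached. Where the restriction would also apply to cases, as genotype availability would, restate the 1,499 on the same basis. Where it defines controls by phenotype, such as painless DPN only, the cases need no matching change, but the remaining respondents should be accounted for.

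The first option changes one number; the second adds a sentence and may change a second number. Neither affects recruitment, questionnaires or data collection.

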### 8.3. Statistical analysis plan (SAP)

The data will be analysed by three separate groups, so three different analysis plans will be developed for different parts of the data analysis:

- 1. The analysis of genetic data will be led by the study coordinator and aims to determine which variants (SNPs) influence the development, severity and remission of NeuP. Genetic variants will be identified using a genome-wide association study approach. Genetic analysis will be based on cohort, disease group and NeuP group and aims to identify genes that identify each group. A description of the genetics analysis will be provided in an analysis plan.
- 2. Machine learning and structural equation modelling (SEM) will be performed by collaborators at the University of Oxford to:

- Produce a ranking of predictive features and determine which ones are most powerful.
- Describe clinical subgroups of patients sharing the same traits and features, which will aid patient stratification.
- Exploit the large phenotypically harmonised cohorts available within PAINSTORM to develop cross-validated predictive models for the clinical subgroups of NeuP identified by the SEM.

PAINSTORM Dundee Epidemiology, will contribute to sophisticated statistical and computational approaches to modelling and quantifying associations with NeuP presence and development, testing their strength and validity. This will adopt two distinct principled approaches: (1) examining all available factors, with a view to understanding the biology of NeuP; and (2) focusing on factors and techniques with the greatest clinical utility, with a view to applying the findings in real-world medical practice. Ultimately, we will develop composite biomarkers signatures for NeuP21, enabling greater understanding of NeuP as well as individualised assessment, and therefore stratified treatment or prevention approach.

3. Questionnaires, biomarkers, lifestyle and health data will be analysed by the study coordinator. The analysis will be based on cohort, disease group and NeuP group and aims to determine factors that influence the presence, development, persistence and remission of NeuP.

## 8.4. Statistical analysis of clinical data

This is an exploratory study that aims to identify predictors of NeuP presence, development, persistence and remission in different disease groups. The three cohorts recruited differ in patient composition, disease group and data collection points. There is therefore no unified primary or secondary endpoint that covers all cohorts. All outcomes are exploratory.

All continuous variables will be summarised using the following descriptive statistics: n (non-missing sample size), number of missing records, mean, standard deviation, median, maximum and minimum.

The frequency and percentages (based on the non-missing sample size) of observed levels will be reported for all categorical measures.

All summary tables will be structured with a column for each disease group and NeuP group and an additional column for the total population relevant to that table/treatment, including any missing observations

## 8.4.1. Summary of baseline data

Baseline data for all analysis are age, sex, weight, height, BMI, SIMD, years in full-time education, working status and household income.

#### 8.4.2. Primary outcome analysis

Not applicable, see section 8.4

## 8.4.3. Secondary outcome analysis

Not applicable, see section 8.4

## 8.5. Subgroup analyses

Subgroups will be specified separately for each cohort and detailed in the SAP. They will include:

- Patients with painful, painless and no peripheral neuropathy (defined using the chronic pain identification, DN4 and EORTC-CIPN20/MNSI screening tools)
- Patients with painful, painless and no neuropathy post chemotherapy (defined using the chronic pain identification, DN4 and EORTC-CIPN20 screening tools)
- Patients with painful, painless and no diabetic neuropathy (defined using the chronic pain, DN4 and MNSI and screening tools)
- Other subgroups as identified in the clinical and genetic analysis

## 8.6. Adjusted analysis

For each cohort and NeuP category, the aim is to build a predictive model of NeuP activity including the major predictive factors.

## 8.7. Participant population

All patients in this study are selected based on medical history data. No treatment will be applied. The patient population for analysis will be all patients included in the study.

## 8.8. Procedure(s) to account for missing or spurious data

Strategies for missing or spurious data will be detailed in the SAP.

#### 9. DATA MANAGEMENT

#### 9.1. Bioinformatics and Data management

Data management will be undertaken in close collaboration with HIC Services, which operates a secure research environment with strong data governance for the provisioning of data to academics and other users to improve healthcare and population health. All services provided by HIC are delivered within a secure environment to ensure data are managed safely and in compliance with Data Protection legislation, and all HIC processes are governed by approved SOPs. The GoDARTS and DOLORisk datasets are already hosted on secure HIC servers, in collaboration with the study investigators. Participants' identities will be shielded from the research team, according to the secure SOPs. Participants will be invited to complete the online or paper version of the PAINSTORM Dundee Epidemiology questionnaire. Paper questionnaires will be returned to HIC with the anonymised study code for identification. Where participants include any personal information this will be separated and stored confidentially, and study data will be entered into the PAINSTORM database.

Access to the database is restricted to approved researchers within the PAINSTORM study and individual accounts are protected by unique username and password. Anonymised data generated from PAINSTORM Dundee Epidemiology will be made available for the PAINSTORM study team to download for analysis on secure computers owned and maintained by the University of Dundee. At the same time, UK Biobank data relating to NeuP, including those

arising from the pain re-phenotyping exercise conducted in 2019-20 and the projected follow-up in 2024 will be downloaded via the secure online Access Management System for analysis in the same environment as the data generated from PAINSTORM Dundee Epidemiology. Access to the computers is through a personalised account, protected by unique username and password, meaning only the PAINSTORM research team will have access to the data. Analytics platforms used will include the Life Sciences Computing (LSC) cluster, maintained by the School of Life Sciences at the University of Dundee, which will be used for all analyses involving genome-wide data. The LSC cluster runs in a UNIX/LINUX environment and has full analytical capability, with the storage capacity (~250Gb) to handle large genome-wide datasets. Access to the LSC cluster is restricted to approved project researchers and data files are restricted by individual-level access permissions. The GoDARTS, UK Biobank and SHARE genetic datasets are already approved for storage on the LSC cluster for other phenotypic studies, but only the PAINSTORM research team will have access to genetic data relating to the PAINSTORM Dundee Epidemiology study.

The main survey will be preceded by a pilot survey of 200 individuals, to test the mailing process and the questionnaire. The intention will be to include the data from the pilot survey with the data from the main survey unless there are substantial revisions to be made to the questionnaire.

Data generated from PAINSTORM Dundee Epidemiology will be linked to genetic, clinical and biomarker data obtained as part of the original recruitment process for the GoDARTS study. Data generated from PAINSTORM Dundee Epidemiology will also be made available in a Trusted Research Environment (TRE; also known as a Safe Haven), maintained by HIC, to allow electronic linkage with routinely collected NHS data including biomarker and clinical variables. It has full analytical functionality including software (e.g. R) and is supported by powerful processing. Remote access to the TRE analytics platform is only available to approved project researchers, after they have signed appropriate agreements, and this provides an efficient multi-user platform for analysing shared or collaborative datasets. Data can only be analysed in the TRE, with remote access available by internet worldwide. No individual-level data can be removed from the TRE, but summary outputs of analysis (e.g. tables) are released, after prompt screening by HIC (to ensure that no potentially identifiable information is included to reduce the risk of accidental disclosure).

Individual level data generated from PAINSTORM Dundee Epidemiology will be made available to approved researchers and collaborators from outside the University of Dundee. These may be from commercial companies and may be from outside of the UK and EU. One of these collaborators is the University of Oxford, led by [name] (PAINSTORM study co-ordinator), who will assess the data for the purposes of curation, analysis and project harmonisation, research governance, quality control and to monitor recruiting progress. Individual patient level data shared with approved collaborators will be in accordance with NHS Data Protection standards and will be anonymised through study PROCHI numbers (generated by HIC to anonymise NHS Scotland Community Health Index numbers), allowing participants'

identities to be shielded from project researchers. Access to the data will be restricted to approved researchers by username and password.

#### 9.2. Data collection tools and source document identification

Study questionnaires will be used as source data.

The study database will be based on the protocol for the study and individual requirements of the investigators. The database is managed in line with all applicable principles of medical confidentiality and UK law on data protection. The Data Controller will be the University of Dundee and the Data Custodian will be the CI.

Development and validation of the study database, quality control and extraction of data will be done according to HIC and TASC procedures. Extracts for analysis will be managed by the CI.

#### 9.3. Access to Data

Direct access will be granted to authorised representatives from the Sponsor, host institution and the regulatory authorities to permit study-related, audits and inspections - in line with participant consent.

## 9.4. Archiving

Archiving will be authorised by the Sponsor following submission of the end of study report. All essential documents will be archived for a minimum of 5 years after end of study, destruction of essential documents will require authorisation from the Sponsor.

#### 10. AUDIT & INSPECTION

The CI, Co-Is and all institutions involved in the study will permit study related monitoring, audits, and REC review. In the event of an audit, the CI will allow the Sponsor, representatives of the Sponsor or regulatory authorities direct access to all study records and source documentation.

## 11. ETHICAL AND REGULATORY CONSIDERATIONS

## 11.1. Research Ethics Committee (REC) review & reports

Before the start of the study, approval will be sought from a REC for the study protocol, and other relevant documents. Substantial amendments that require review by REC will not be implemented until the REC grants a favourable opinion for the study.

All correspondence with the REC will be retained in the Trial Master File. A copy of all REC reports will be submitted to the Sponsor.

An annual progress report will be submitted to the REC within 30 days of the anniversary date on which the favourable opinion was given, and annually until the study is declared ended. It is the Chief Investigator's responsibility to produce the annual reports as required.

The Chief Investigator will notify the REC of the end of the study. If the study is ended prematurely, the Chief Investigator will notify the REC, including the reasons for the premature termination

Within 1 year after the end of the study, the Chief Investigator will submit a final report with the results, including any publications/abstracts, to the REC

#### 11.2. Peer review

Extensively reviewed by the funders as part of the award process, UK Research and Innovation (Medical Research Council), Versus Arthritis and Eli Lilly, via their Advanced Pain Discovery Platform.

#### 11.3. Public and Patient Involvement

The PAINSTORM proposal was developed by a team of patients, clinicians and researchers, inspired by research and conversations with people living with NeuP. Patient partners have actively shaped content to ensure unmet needs have been addressed. Discussions with people living with NeuP were held to uncover relevant research priorities for PAINSTORM, centred on individuals' experience of pain and the best way to assess pain.

Three individuals have volunteered to be patient partners for PAINSTORM Dundee Epidemiology on the main research team (named in the protocol contributors section). The protocol has been reviewed by these patient partners. A patient partner will attend research ethics committee meetings so that they can describe what is being done with patients in patient/public facing materials (e.g., information leaflets). All information material, such as participant information sheets and lay summaries, have been written in plain English and reviewed by the patient partners to ensure people can find out what they want to know in an understandable way. The patient partners will be invited to become a member of the Trial Management Group and attend meetings to give their input into how the study is being carried out. Patient partners will be involved in analysis and interpretation of findings to ensure that emerging knowledge makes sense to those with lived experience.

## 11.4. Regulatory Compliance

The study will not commence until favourable REC opinion is obtained. Before the site can enrol participants into the study, the Cl/Co-ls or designee will ensure that appropriate approvals (NHS R&D) from the participating organisation is in place.

For any amendment to the study, the CI or designee, in agreement with the sponsor, will submit information to the appropriate body in order for them to issue approval for the amendment. The CI or designee will work with the site (R&D department at NHS site as well as the study delivery team) so they can put the necessary arrangements in place to implement the amendment to confirm their support for the study as amended.

## 11.5. Protocol compliance

Prospective, planned deviations or waivers to the protocol are not allowed and must not be used e.g. it is not acceptable to enrol a participant if they do not meet the eligibility criteria or restrictions specified in the study protocol. Accidental protocol breaches can happen at any

time. They must be adequately documented on the relevant forms and reported to the CI and Sponsor immediately.

Breaches from the protocol which are found to frequently recur are not acceptable, will require immediate action and could potentially be classified as a serious breach.

In the event that there is a breach of the protocol, the nature of and reasons for the breach will be recorded in the TMF and documented in the study TASC Breach Log and reported to Sponsor via the breach reporting process.

As the questionnaires are self-complete, where participants do not complete all questions of the PAINSTORM Dundee Epidemiology questionnaire or do not complete the follow up questionnaires, these will not be recorded as breaches. Where there is data which is not available for some participants this will not be recorded as a breach. Procedures to account for missing data will be detailed in the SAP.

